in New York City. ENG samples will be collected, frozen, and batch-shipped. The subject population will be healthy, HIV-negative women using Nexplanon®/Implanon®, with the anticipation that the findings will be applicable to HIV-infected women. There is limited data regarding the use of the etonogestrel implant in obese women. While two small studies found lower etonogestrel concentrations in obese women than normal weight women, the differences were not statistically significant[16, 17]. Overweight and obese women using the etonogestrel implant do not experience contraceptive failures more frequently than overweight or obese women using an intrauterine device[18]. We will limit enrollment to women with a BMI <30 kg/m² so as to limit any effect morbid obesity may have on etonogestrel concentrations. We expect that the study will take a total of 12 months to complete. A screening visit to confirm eligibility will occur prior to initiation of study visits.

Screening: Potential subjects will be identified by their treating providers as meeting basic eligibility criteria (appropriate age and currently using Nexplanon®/Implanon®). Each candidate will be informed of the study purpose and design, and will be given contact information for study personnel if she is interested in enrolling. With her permission, the potential subject's contact information will also be forwarded to study personnel, who will then contact her by phone. During a phone interview, details of the study will be discussed with her, after which she will be asked to come to the Bayview CRU for an in-person interview. During this visit, she will be asked to read and sign the approved consent form, undergo a history and physical exam, and have baseline laboratory tests performed (hematologic and metabolic panels as described in Inclusion Criteria, serum HIV, urine pregnancy test), as well as a baseline ultrasound to ensure her ovaries are detectable. Study personnel will review the results of the laboratory tests, and if all results are in the specified ranges, the subject will be contacted to schedule the start of the study protocol.

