Data collection: After successful screening, women will be asked to take 14 days of EFV in a once-nightly 400 mg regimen. We will collect blood samples for baseline ENG concentration on the day participants begin taking EFV, before the first dose (Day 1, times 0 hour, 1 hour, and 2 hours). The first dose of EFV will be taken in the evening of Day 1, and the next blood sample for ENG concentration will be drawn twelve to twenty hours after the first dose of EFV. (For example, if a participant takes her first dose of EFV at 10 PM on Day 1, she will be asked to return to the CRU between 10 AM and 6 PM on Day 2.) We will then obtain subsequent samples every 3 to 4 days (+/- 1 day) for the remainder of the two week EFV course and for 4 additional weeks (through Week 6 of study participation). This is a total of 14 outpatient visits, including screening. All serum samples will be analyzed for concentrations of ENG, which will be used to derive the ENG area under the concentration-time curve (AUC), the maximum and minimum observed serum drug concentration (C_{max}, C_{min}), and the apparent average serum concentration at steady-state (C_{ss,avg}) using WinNonlin®. EFV concentrations will be determined from plasma samples obtained at 2 timepoints during EFV administration, and measured using a validated LC/MS/MS assay in the Clinical Pharmacology Analytical Laboratory of the Johns Hopkins Hospital.

Table 1: Participant Visit Schedule and Timing of Study Assessments

Visit	Screening	Study Entry			Week 1		Week 2		Week 3		Week 4		Week 5		Week 6	
		1			2	7	11	14	18	21	25	28	32	35	39	42
Serum Tests		0 hr	1 hr	2 hr												
ENG		X	X	X	X	X	X	X	X	X	X	X	X	X	X	X
EFV					X			X								
FSH		X			X	X	X	X	X	X	X	X	X	X	X	X
LH		X			X	X	X	X	X	X	X	X	X	X	X	X
Estradiol		X			X	X	X	X	X	X	X	X	X	X	X	X
Progesterone		X			X	X	X	X	X	X	X	X	X	X	X	X
Safety Labs	X															X
UPT	X															X
HIV	X															X
TVUS	X				X	X	X	X	X	X	X	X	X	X	X	X
CM	X				X	X	X	X	X	X	X	X	X	X	X	X

Date: January 5th, 2017

Principal Investigator: [name], MPH

Application Number: NA_00087585

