Secondary endpoints will be serum markers of ovulation (estradiol [E₂], progesterone [P], follicle stimulating hormone [FSH], and luteinizing hormone [LH]), as well as evidence of ovulation on cervical mucus exam and transvaginal ultrasound (presence and subsequent disappearance of a dominant follicle >15 mm diameter)[19]. Blood for hormone assays will be drawn at the Bayview CRU at the same time as samples for ENG and EFV. During these visits participants will also undergo a pelvic exam for cervical mucus assessment, and a pelvic ultrasound to look for ovarian follicular activity. Monitoring throughout the study will allow us to compare ovarian activity across time points through both ultrasound visualization and ovarian hormone testing (E₂ and P). Changes in cervical mucus quality secondary to the progestin activity of ENG provide secondary contraceptive effects that may be maintained even if ovulation occurs. Continued monitoring for several weeks after cessation of EFV will allow us to follow subjects for the equivalent of a normal menstrual cycle, to ascertain whether either contraceptive effect (ovulation suppression or cervical mucus quality) was altered. Urine pregnancy tests may be repeated throughout the duration of the study as needed.

Ultrasounds and venipuncture for LH, FSH, E₂ and P levels will occur in the CRU. A total of 20 mL of venous blood will be collected for each outpatient visit. FSH, LH, E₂, and P assays will be performed by the CRU at JHU. FSH and LH will be measured using the automated immunoradiometric assay (IRMA) system. Assay sensitivity of LH assays is 0.07 mIU/ml; assay sensitivity of FSH assays is 0.2 mIU/ml. P will be measured using an automated immulite chemiluminescent assay system. Assay sensitivity of the P assay is 0.05 ng/ml. E₂ will be measured via an ultra-sensitive competitive binding radioimmunoassay with sensitivity of 2.2 pg/ml. The EFV assay will be performed through the Johns Hopkins Hospital Clinical Pharmacology Analytical Lab, and will be measured via LC-MS/MS assay with a lower limit of quantification of 0.5 ng/ml.

An assay for ENG is not commercially available, but the Irving Institute for Clinical and Translational Research at the Columbia University Medical Center in New York has developed a validated assay. ENG concentrations will be measured by LC-MS/MS, and the assay has a lower limit of quantification of 50 pg/ml.

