Transvaginal ultrasound (TVUS) will be performed using high-resolution machines (Sonosite Edge, SonoSite, Inc., Bothell, WA) in our clinic to monitor follicular development. Follicular diameter will be calculated by averaging the mean of the length and width in both the sagittal and transverse plane. Follicles measuring ≥ 10 mm will be considered dominant preovulatory follicles, and only follicles measuring ≥ 10 mm will be recorded[20]. Ovulation will be defined as the disappearance of a follicle ≥ 15 mm in diameter that was observed the visit before. We will collect cervical mucus using an endocervical aspirator, and evaluate the sample for consistency, ferning, Spinnbarkeit, and cellularity. Each variable will be scored on a 0 to 3 point scale according to WHO guidelines. A total score of 9 to 12 will indicate mucus conditions favorable to sperm penetration[21].

Recruitment: Subjects will be recruited from the general gynecology office in JHOC and practices affiliated with JHBMC. We will recruit patients known to be using Nexplanon®/Implanon®. Written notices advertising the study will be placed in the gynecology offices as well as in other affiliated primary care offices. We will also place advertising notices throughout Johns Hopkins institutions including the School of Nursing and the School of Public Health.

b. Study duration and number of study visits required of research participants.

Date: January 5th, 2017

Principal Investigator: [name], MPH

Application Number: NA_00087585

We anticipate that the study will take 12 months to complete. Participants will be enrolled for a total of 6 weeks (2 weeks taking EFV, and 4 weeks additional follow-up), during which time they will complete 14 visits including a screening visit. After enrollment, visits will occur twice weekly.

c. Blinding, including justification for blinding or not blinding the trial, if applicable.

Not applicable in this pilot pharmacokinetic study

d. Justification of why participants will not receive routine care or will have current therapy stopped.

Not applicable.

e. Justification for inclusion of a placebo or non-treatment group.

Not applicable.

f. Definition of treatment failure or participant removal criteria.

Treatment failure is not applicable to this study as efavirenz is being given to healthy volunteers and not part of an HIV treatment regimen. A participant will be removed from the study under the following circumstances:

- She misses more than three study visits

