- Serum hormonal markers of ovulation (P, E₂, LH, FSH)
- Presence of dominant follicle(s) on transvaginal ultrasound during and after EFV dosing
- Change in cervical mucus quality suggesting ovulation during and after EFV dosing

- c. Statistical plan including sample size justification and interim data analysis.

Sample size: We hypothesize that during co-administration of the ENG implant and reduced-dose EFV, we will detect a decrease in serum ENG concentrations, but that overall contraceptive effect will be maintained. We do not anticipate that any subjects will have a drop in ENG concentration below the threshold needed for ovulation suppression (90 pg/mL)[8]. Using a two-sided Wilcoxon test, a sample size of 15 will have 80% power (with an alpha of 0.05) to detect a 20% difference in ENG concentration between women taking EFV and historical controls. We plan to enroll 18 women to account for a potential 20% drop-out rate.

Data Analysis: We will calculate area under the curve (AUC) and maximum and minimum concentrations of each drug (C_{max} and C_{min}), as noted above. For hormone markers (LH, FSH, E₂, P) we will evaluate change over time as well as whether pertinent threshold levels are reached that could indicate that ovulation has occurred. All serum tests will be evaluated through the Johns Hopkins Division of Clinical Pharmacology, with the exception of etonogestrel concentrations as this assay is not widely available. Serum samples will be frozen and shipped to the Irving Institute for Clinical and Translational Research at Columbia University Medical Center in New York City, which will perform the etonogestrel assay.

Interpretation: If the pharmacokinetic parameters for etonogestrel that are seen in this interaction study are consistent with those published in the literature (less than 30% difference), we will conclude that there is no significant interaction between ENG and reduced-dose EFV. This would support the assertion that Nexplanon®/Implanon® is a safe and effective option for HIV-infected women taking reduced-dose EFV who desire long-acting reversible contraception. However, if two or more women out of a sample of 15 breach the threshold concentration needed for ovulation suppression, it will indicate a statistically and clinically significant decrease in ENG concentration and potential for decreased contraceptive efficacy.

Date: January 5th, 2017

Principal Investigator: [name], MPH

Application Number: NA_00087585

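### Follicles below 10 mm go unrecorded and the listed ultrasound outcome is presence only, so a partial loss of ovarian suppression may go unseen, to an extent the documents do not let one compute

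*Combined protocol and SAP*

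**What the plan says.** In section 4a, the transvaginal ultrasound paragraph defines a continuous measurement: "Follicular diameter will be calculated by averaging the mean of the length and width in both the sagittal and transverse plane". It then sets a floor: "Follicles measuring ≥ 10 mm will be considered dominant preovulatory follicles", and "only follicles measuring ≥ 10 mm will be recorded". Ovulation is an event based on size: "Ovulation will be defined as the disappearance of a follicle ≥ 15 mm in diameter that was observed the visit before".

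Section 7b lists "Presence of dominant follicle(s) on transvaginal ultrasound during and after EFV dosing". Because dominant means 10 mm or more in the ultrasound paragraph, this outcome amounts to whether any follicle was recorded.

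On the purpose of the scans, section 4a says: "Monitoring throughout the study will allow us to compare ovarian activity across time points through both ultrasound visualization and ovarian hormone testing". The sentence goes on to name estradiol and progesterone as the hormones.

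Table 1 schedules a scan at screening, none on Day 1, and one at each visit from Day 2 to Day 42. Section 4a gives the reason for the screening scan: "as well as a baseline ultrasound to ensure her ovaries are detectable".

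The data-analysis paragraph of 7c analyses LH, FSH, estradiol and progesterone both as change over time and against thresholds. For ultrasound it names no test, no unit of analysis (scan, period or woman) and no diameter summary.

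**The concern.** The first secondary objective (section 2) asks whether pharmacodynamic changes point to a raised risk of ovulation. That is wider than counting ovulations. Section 7c expects etonogestrel (ENG) to fall while contraceptive effect is maintained, so a partial loosening of ovarian suppression is a result the study could meet. Follicle diameter is the scan measure that could show it by degrees.

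The plan loses this information in two ways. The recording floor removes every diameter below 10 mm, and nothing done at analysis can bring these back. The listed outcome then ignores the diameters that were kept. The second loss can be repaired at analysis. The first must be changed before scanning.

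**Working it through.** **1. Scans available.** Table 1 gives Days 2, 7, 11 and 14 on efavirenz (4 scans) and Days 18, 21, 25, 28, 32, 35, 39 and 42 afterwards (8 scans): 4 + 8 = 12 on study, plus screening. The Day 2 visit falls 12 to 20 hours after the first dose, so screening is the only pre-efavirenz scan.

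**2. What the rules keep.** These are illustrative largest diameters at two successive visits.

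| Change | Recorded | Presence (7b) | Ovulation rule |
|---|---|---|---|
| 5 to 9 mm | nothing, nothing | no, no | no |
| 9 to 11 mm | nothing, 11 | no, yes | no |
| 11 to 14 mm | 11, 14 | yes, yes | no |
| 16 mm, then gone | 16, nothing | yes, no | yes |

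The first row is lost for good. The third is on file, but the listed outcome does not use it.

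**3. The plan's own figure.** The only power statement (7c) is 80% with 15 women for a 20% difference in ENG concentration. None is made for ultrasound, so there is nothing to reproduce. The documents give no follicle-size distribution, so every size and SD below is an assumption.

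**4. One early scan against one late scan.** Assume 15 women, between-woman SD 3 mm, within-woman SD 3.5 mm, normal diameters and starting means of 6 to 12 mm.
- Total SD = √(3² + 3.5²) = 4.61 mm. From a mean of 8 mm, growth of 3 mm moves the chance of 10 mm or more from 1 − Φ(2/4.61) = 33% to Φ(1/4.61) = 59%, or about 5.0 to 8.8 women of 15.
- Exact McNemar at two-sided 0.05 needs at least six women switching, all one way: 2 × 0.5⁵ = 0.063, 2 × 0.5⁶ = 0.031.
- For diameter, the SD of a difference is 3.5√2 = 4.95 mm. Growth of 3 mm is 3/4.95 = 0.61 SD; growth of 4 mm is 0.81 SD.
- Simulated power at 3 mm: about 8% to 18% for exact McNemar on presence, 26% to 52% for a signed-rank test with sizes kept only at 10 mm or more, and 55% to 58% for a signed-rank test on full diameter. At 4 mm: 14% to 35% for McNemar against about 80% for full diameter.
- With no true change, McNemar rejects in 0.2% to 1.0% of runs and the signed-rank test in 4.6% to 5.2%. Part of the gap is therefore the conservatism of the test. The mid-p version reaches 19% to 30% at 3 mm.

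**5. Four scans against four.** Assume log-normal diameters, between- and within-woman log SDs of 0.30 and 0.35, and a 30% rise. Columns: (a) signed-rank test on mean diameter per period; (b) the same with values below 10 mm set to 10; (c) signed-rank test on the share of scans with a follicle of 10 mm or more; (d) any such follicle per woman per period, exact McNemar.

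| Median, mm | (a) | (b) | (c) | (d) |
|---|---|---|---|---|
| 4 | 0.89 | 0.08 | 0.06 | 0.04 |
| 6 | 0.88 | 0.53 | 0.56 | 0.18 |
| 8 | 0.88 | 0.72 | 0.67 | 0.08 |
| 10 | 0.88 | 0.81 | 0.65 | 0.01 |
| 12 | 0.90 | 0.85 | 0.54 | 0.00 |

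The share of (a) that is retained is, for example, 0.53/0.88 = 60% for (b) at 6 mm. Over log SDs from 0.20/0.25 to 0.40/0.50:
- (b), the recording floor alone: 0% to 31% at 4 mm, about 60% to 66% at 6 mm, 78% to 94% at 8 mm, and 88% to 99% at 10 to 12 mm.
- (c), presence scan by scan: 0% to 30% at 4 mm, and about 58% to 91% at 6 to 12 mm.
- (d), one yes/no per woman per period: at most 36%, the best case being 0.36/0.99.

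The pattern follows from the total log SD, √(0.30² + 0.35²) = 0.46. At a median of 4 mm, only 1 − Φ(ln(10/4)/0.46) = 2% of scans reach 10 mm, so presence is almost always no. At 10 mm, half of scans do, and most women show one such follicle in both periods.

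**6. Unequal windows.** With no true change, test (d) rejected in up to 37% of runs for one scan against four, and up to 82% for one against twelve, because more scans give more chances of a yes. An ever-present comparison of screening with later periods would mislead in the opposite direction.

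**The case against.** The strongest reply is that the objective concerns ovulation risk, and follicles of 10 mm and 15 mm are the events the plan chose for it, with a cited source for the 10 mm rule. Continuous ovarian measures are already planned: four hormones at 13 visits, analysed as change over time. The study is a pilot sized on ENG, and no ultrasound power is claimed. All of this stands, and it limits how much depends on the scans.

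Three stronger readings are tempting and are not supported.
- A reader might infer that most of the power of the 12 scans is thrown away. The documents fix neither follicle sizes nor a unit of analysis. The single-pair calculation uses two scans and a conservative test, and scan-by-scan presence keeps more than half the power at medians of 6 mm or more.
- A reader might infer that a 10 mm follicle counts the same as a 20 mm one. That is true of the presence outcome, but the plan as a whole keeps sizes of 10 mm or more and needs them for the 15 mm ovulation rule.
- A reader might infer that a null scan result will be taken as maintained suppression. No section says so. The interpretation paragraph in 7c rests on ENG parameters and the ENG threshold.

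A simple late-minus-early difference in diameter would also be a poor replacement. Diameter falls when a follicle ruptures, and the earliest on-study scan already follows a dose.

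What the reply does not meet is the floor itself. Hormones do not restore an unrecorded diameter, and 4a names ultrasound as one of the two ways in which ovarian activity will be compared.

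**Conclusion.** The point holds in a limited form. Growth below 10 mm leaves no record, and the listed outcome does not use the diameters that are kept, so the scans are weaker than they need be for the comparison over time that 4a describes.

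The loss of power is real in direction but not computable in size from the documents. Under the assumed sizes it ranges from modest to nearly complete. With presence analysed scan by scan and medians of 6 to 12 mm, the loss is roughly 9% to 42% of full-diameter power. It is at least 64% for one yes/no per woman per period, and at least 69% for scan-by-scan presence or the floor alone at a median near 4 mm. These figures rest on 15 women, equal windows of four scans, log-normal diameters and a 30% rise. The direction does not depend on them.

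**What to change.** - **Section 4a:** replace the recording floor with a rule that the diameter of the largest follicle in each ovary is recorded at every scan, including screening, whatever its size.
- **Sections 7b and 7c:** add a within-woman repeated-measures comparison of largest follicle diameter over all scans, with screening identified as the only pre-efavirenz value. A simpler alternative is peak diameter in windows with equal numbers of scans. Table 1 already gives three windows of four: Days 2 to 14, 18 to 28 and 32 to 42.
- **Reporting:** give ovulation by the 15 mm disappearance rule and presence at 10 mm or more alongside, so that a fall in diameter after ovulation is not read as suppression. Analyse presence scan by scan.
- **If the floor stays:** treat diameters below 10 mm as left-censored at 10 mm in the model.
- **Definitions:** reconcile the secondary-endpoint paragraph of 4a, which attaches dominant to a follicle above 15 mm, with the ultrasound paragraph, which uses 10 mm or more for dominant and 15 mm or more for ovulation.

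The cost is one extra field on the scan form and a little more analysis. No extra scan, visit or reader is needed.

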Accumulating evidence suggests a significant effect of efavirenz on systemic concentrations of etonogestrel when the two medications are taken together. Published studies have focused on changes in serum concentrations of etonogestrel and serum progesterone concentrations as a marker of ovulation, but they have not evaluated the other ways the etonogestrel implant likely prevents pregnancy (i.e. changes in endometrium and cervical mucus). It remains unclear whether a lower dose of efavirenz will lead to a similar decrease in etonogestrel concentrations. We propose this study to formally evaluate the interactions that may exist between these two drugs. Among the antiretroviral drugs that could affect the activity of ENG, we selected EFV for this study because of the case reports mentioned above as well as its widespread use as part of first-line antiretroviral regimens. We will use a lower dose than that currently used in clinical practice (400 mg orally each night, instead of the standard dose of 600 mg).

- Justification and safety information if FDA approved drugs will be administered for non-FDA approved indications or if doses or routes of administration or participant populations are changed.

This pilot study is being conducted to determine if reduced-dose EFV decreases the efficacy of ENG delivered by the contraceptive implant to the point where HIV-positive women taking reduced-dose EFV

Date: January 5th, 2017

Principal Investigator: [name], MPH

Application Number: NA_00087585

who are also relying on this contraceptive are at increased risk of unintended pregnancy. The use of EFV in this protocol is therefore off-label in that EFV will be given to HIV-uninfected women. EFV is indicated only for use in combination with other antiretroviral drugs in the treatment of HIV. Consequently, it would be very difficult to isolate the effects of EFV on ENG in women taking combination antiretroviral therapy due to the potential other drug interactions that may be present.

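### The stated ovulation definition uses ultrasound alone, and no rule joins it to the progesterone drawn at the same visits

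*Combined protocol and SAP*

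**What the plan says.** The transvaginal ultrasound paragraph of section 4a states: "Ovulation will be defined as the disappearance of a follicle ≥ 15 mm in diameter that was observed the visit before". No hormone condition is attached. The same paragraph sets a recording floor: "only follicles measuring ≥ 10 mm will be recorded". Earlier in section 4a, the paragraph on secondary endpoints describes ultrasound evidence of ovulation as "presence and subsequent disappearance of a dominant follicle >15 mm diameter". That is a strict inequality, and it does not refer to the preceding visit.

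Progesterone is collected alongside the scans. Table 1 shows it on Day 1 and at every scan visit from Day 2 to Day 42, and section 4a says: "Blood for hormone assays will be drawn at the Bayview CRU at the same time as samples for ENG and EFV". Section 7b lists "Serum hormonal markers of ovulation", naming progesterone among them. Section 4a says that ovarian activity will be compared using both ultrasound and estradiol and progesterone. Section 7c says that the hormones will be examined for change over time and for reaching levels that could indicate ovulation. Neither place gives a level, a time window relative to follicle disappearance, or a rule for cases where scan and hormone disagree.

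Under section 4f a participant is removed only after missing more than three visits, so up to three may be missed.

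**The concern.** A definition that rests on one scan sign can err in two directions. Because of the 10 mm floor, a follicle that has shrunk and one that has ruptured can leave the same blank in the record. Because scans are days apart, a follicle can cross 15 mm and rupture without ever being seen at that size. A missed visit also leaves it unclear what the preceding visit is.

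Progesterone could help to settle many of these cases. The protocol recognises its role: section 6, describing published studies, refers to "serum progesterone concentrations as a marker of ovulation". Without a rule fixed in advance, a woman positive on one marker and negative on the other could be classified either way once the data are seen.

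Risk of ovulation is the first secondary objective in section 2. Section 7c expects contraceptive effect to be maintained, so missed ovulations would lean towards the expected answer. In 15 women, one event is 1/15 = 6.7 percentage points.

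**Working it through.** The plan states no sensitivity or error rate for detecting ovulation, so there is no figure to reproduce.

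**Inputs from the documents.** Table 1 scan days after entry are 2, 7, 11, 14, 18, 21, 25, 28, 32, 35, 39 and 42. The 11 gaps are 5, 4, 3, 4, 3, 4, 3, 4, 3, 4 and 3 days, which total 40 days. The screening scan is left out because its interval to Day 2 is not fixed.

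**Assumptions, not in the documents.** Ovulation is equally likely at any time from Day 2 to Day 42. The follicle is at 15 mm or more for T days before rupture. Progesterone stays above a chosen cut-off for L days.

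**Missed ovulations, full attendance.** The rule sees an ovulation only if a scan fell within the T days before rupture. The share missed is 1 − Σ min(gap, T) / 40.

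| T (days) | Σ min(gap, T) | Missed |
|---|---|---|
| 1 | 11 × 1 = 11 | 72.5% |
| 2 | 11 × 2 = 22 | 45% |
| 3 | 11 × 3 = 33 | 17.5% |
| 4 | 4 + 5 × 4 + 5 × 3 = 39 | 2.5% |
| 5 or more | 40 | 0% |

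**Missed ovulations, three interior scan visits absent.** The preceding visit is read as the last one attended. The 11 gaps merge into 8, all at least 3 days long, still totalling 40.

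- T = 2: 1 − 16/40 = 60%.
- T = 3: 1 − 24/40 = 40%.
- T = 4 and T = 5: about 26% and 19%, averaged over randomly chosen absent visits by simulation.

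**False positives.** Set the definition beside the recording floor. A follicle of at least 15 mm at one visit and under 10 mm at the next has no entry at the second visit, and so can be read as having disappeared. This requires a fall of more than 5 mm within one gap. A follicle caught on the way down, for example at 13 mm, is recorded and does not meet the rule at the following scan. The documents give no frequency for such falls, so no rate can be computed.

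**What progesterone at the same visits could add.** The share of ovulations with at least one sample in the raised window is Σ min(gap, L) / 40. This gives 33/40 = 82.5% for L = 3, 39/40 = 97.5% for L = 4, and 100% for L of 5 or more, with full attendance.

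**The case against.** A reader might infer that the plan ignores progesterone. The documents do not support that. Sections 4a and 7c plan a parallel hormone assessment, and section 7b lists progesterone as an outcome. The definition also sits in the ultrasound paragraph and can be read as the ultrasound criterion, one marker among several. This is fair as far as it goes. But it is the only statement of what counts as ovulation, and nothing says how the parallel markers alter that call.

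A reader might also infer that large errors in both directions are certain. They are not. The share missed runs from 72.5% to 0% depending on an assumed duration, and it vanishes at 5 days or more with full attendance. The false-positive route needs a sharp fall within one gap and needs a blank entry to be taken as disappearance, which the protocol does not say outright. These are possible errors of unknown frequency.

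Finally, the primary outcome is etonogestrel concentration. The interpretation rule in section 7c turns on a 30% pharmacokinetic difference and on breaches of the suppression threshold, not on an ovulation count. This objection stands and limits the weight of the point.

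**Conclusion.** The point holds in a limited form. The stated definition is ultrasound-only, the progesterone threshold is unnamed, and no rule combines or reconciles the two. As written, the definition can count a regressed follicle as an ovulation and can miss a rupture between scans. How many are missed depends on assumed durations and on attendance. The false-positive rate cannot be estimated.

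The main etonogestrel conclusion is untouched. What is at risk is the classification of a key secondary endpoint in about 15 women, where one misclassified woman decides whether any ovulation is reported if hers is the only event. The change is worth making because the samples and scans that it needs are already planned.

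**What to change.** Amend the definition as follows, before hormone results are reviewed. The study is unblinded, so the protection lies in this order of steps.

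- Set a progesterone cut-off from the assay laboratory's luteal range and write it into the plan.
- **Confirmed ovulation:** a follicle of at least 15 mm at the last attended visit has disappeared, with progesterone above the cut-off at that visit or the next.
- **Probable ovulation:** progesterone rises above the cut-off without a qualifying follicle having been seen.
- **Unconfirmed:** the follicle disappears without a progesterone rise.
- **Indeterminate:** the event is first seen on Day 42 or spans a missed visit, unless progesterone resolves it.
- Keep recording any follicle that has reached 10 mm after it falls below that size.
- Report the ultrasound-only rule as a sensitivity analysis.
- Reconcile the two inequalities in section 4a (more than 15 mm, and at least 15 mm).

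The cost is wording and one case-report field, with no extra visits, scans or samples. Some events will carry a less definite label. The remedy is also incomplete, because a missed visit loses the progesterone sample as well as the scan, and Day 42 has no following visit.
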